6 ADVERSE EVENTS

The study is considered to carry a low risk of potential adverse events (https://livenapierac.sharepoint.com/sites/rio/research-policy-guidelines/Research%20%20Innovation/Research%20Integirty/Adverse%20Events

Date: 30/5/2022 Version: 6

%20Reporting%20SOP.pdf), but a risk assessment has been completed [Appendix 14].

There is a possibility that the participant may experience negative emotions when being told the news of suspected AF. In this instance the study nurse will arrange for the participant to be followed up by a GP/cardiology consultant.

7 OVERSIGHT ARRANGEMENTS

INSPECTION OF RECORDS (where appropriate)

Investigators will permit study monitoring and audits by Edinburgh Napier University where relevant. In the event of audit or monitoring, the principal investigator agrees to allow representatives of the University audit team direct access to all study records and source documentation.

8 ETHICAL CONSIDERATIONS and GOOD CLINICAL PRACTICE

ETHICAL CONDUCT 8.1

The study will be conducted in accordance with the principles of the International Conference on Harmonisation Tripartite Guideline for Good Clinical Practice (ICH GCP). Before the study can commence, all required approvals will be obtained and any conditions of approvals will be met.

8.2 INVESTIGATOR RESPONSIBILITIES

The principal investigator will be responsible for the overall conduct of the study and compliance with the protocol and any protocol amendments.

8.2.1 Informed Consent

Phase 1: patient screening and Phase 2: healthcare professionals' interview:

The principal investigator is responsible for ensuring informed consent is obtained before any protocol specific procedures are carried out. The decision of a participant to participate in research is voluntary and should be based on a clear understanding of what is involved.

The participant will be given every opportunity to clarify any points they do not understand and, if necessary, ask for more information. Details of the principal

Date: 30/5/2022 Version: 6

investigator will be included in the Participant Information Sheet to facilitate this. The participant will have sufficient time to consider the information provided. information will emphasise that the participant may withdraw from the study at any point.

8.2.2 Confidentiality

Phase 1: patient screening:

Three copies of the consent form will be made. One will be given to the patient, one will be put in the patient's dental file, and the original will be put in the Investigator Site File, which will be stored securely in the Dental Clinical Research Facility. Participant identifiable data will be entered directly into a Microsoft excel document containing personal contact and GP details, linked to unique participant ID (PID), stored on the Edinburgh Napier University X drive by the research nurse onsite at the Dental Hospital using a secure managed University laptop. All other study data will be entered directly into an anonymised Microsoft Excel document identifiable only via the PID on the Edinburgh Napier University X drive in a folder allocated to this study. There will be no stored paper records of participant data collection forms by Edinburgh Napier University and the PID will be the only identifier entered onto the KardiaMobile system.

Access to electronic data will be limited to study research group membership, which will be set up with information services support on the University X drive. The principal investigator will decide whether users require read-only or read write access. Offcampus access will be via the Virtual Desktop System. Data will not be stored on individual computers or laptops. Any portable electronic devices (including audio recording devices) will be encrypted in line with the University data protection policy. Transfer of patient BPE rating will be by a secure data transfer protocol as outlined in a data sharing agreement that will be in place prior to the start of the study.

Phase 2: healthcare professionals' interview:

All data will be anonymized during transcription and participants will be given a study ID to ensure that they cannot be recognised. Field notes will be typed up and paper copies destroyed. All transcribed and field note documents will be stored records won the Edinburgh Napier University secure research drive (University X drive). All consent

Date: 30/5/2022 Version: 6

forms will be stored electronically on the x-drive in a password protected folder that is separate to data.

Access to electronic data will be limited to study research group membership, which will be set up with information services support on the University X drive. The principal investigator will decide whether users require read-only or read write access. Off-campus access will be via the Virtual Desktop System. Data will not be stored on individual computers or laptops. Any portable electronic devices (including audio recording devices) will be encrypted in line with the University data protection policy. If any sensitive data needs to be transmitted electronically, this will be done via encrypted email.

There will be no identifiable data, therefore participants will not need to provide written permission for the release of, or access to, any confidential information. The principal investigator and study team will not disclose or use for any purpose other than performance of the study, any data, record, or other unpublished, confidential information disclosed for the purpose of the study. Participants must provide written permission for the release of, or access to, any confidential information. The principal investigator and study team will not disclose or use for any purpose other than performance of the study, any data, record, or other unpublished, confidential information disclosed for the purpose of the study.

8.2.3 Data Protection

The study protocol includes a data management plan [Appendix 15] which details the collection, transfer, storage, processing, and disclosure of personal information related to the study. The study will collect identifiable data; therefore a privacy impact assessment has been completed and approved by Edinburgh Napier University governance team, and privacy notices will be provided to participants in both elements of the study.

All investigators involved with this study will comply with the requirements of the UK-General Data Protection Regulation and Data Protection Act 2018 and will uphold the legislation's core principles. Access to collated participant data will be restricted to individuals from the research team and representatives of regulatory authorities.

Computers used to collate data will have encryption or limited access measures via usernames and passwords.

Edinburgh Napier

Published results will not contain any personal data that could allow identification of individual participants.

9 STUDY CONDUCT RESPONSIBILITIES

9.1 PROTOCOL AMENDMENTS

Any changes in research activity, which involve a change in the study protocol (except those required to manage an urgent safety issue), must be reviewed and approved by the principal investigator. All study amendments will be submitted to a School of Health and Social Care representative for review and authorisation before being submitted in writing to NHS REC, and NHS local R&D for approval prior to participants being enrolled into an amended protocol.

9.2 SERIOUS BREACH OF PROTOCOL REQUIREMENTS

A serious breach is a breach which is likely to effect to a significant degree:

- (a) the safety or physical or mental wellbeing of the participants in the study; or
- (b) the scientific value of the study.

If a potential serious breach is identified by the principal investigator or delegates, Edinburgh Napier University School of Health and Social Care must be notified within 24 hours as per Edinburgh Napier University Adverse Events Standard Operating Procedures. It is the responsibility of the School of Health and Social Care to assess the impact of the breach on the scientific value of the study, to determine whether the incident constitutes a serious breach and report to the relevant research ethics committee/s as necessary.

9.3 STUDY RECORD RETENTION

All study documentation will be kept for a minimum of 10 years from the protocol defined end of study point. Data will then be destroyed in line with Edinburgh Napier University guidance. The study co-coordinator will diarize the data destruction date.

9.4 END OF STUDY

The end of study is defined as all data collection and analysis being completed.

The investigators have the right at any time to terminate the study for administrative reasons.

9.5 INSURANCE AND INDEMNITY

Edinburgh Napier University is responsible for ensuring proper provision has been made for insurance or indemnity to cover their liability and the liability of the Chief Investigator and staff.

The following arrangements are in place to fulfil the Universities responsibilities:

 The Protocol has been designed by the principal investigator and researchers employed by the University and collaborators. The University has insurance in place (which includes no-fault compensation) for negligent harm caused by poor protocol design by the principal investigator and researchers employed by the University.

10 REPORTING, PUBLICATIONS AND NOTIFICATION OF RESULTS

10.1 AUTHORSHIP POLICY

Ownership of the data arising from this study resides with the study team.

12.11 Appendix 11: Patient Screening Document Phase 1 (Version 3:16/8/2022)

	Participant ID:			
	Name			
	Address			
	Postcode (IMD):			
	Date of Birth:			
	Telephone Number:			
	Registered GP:			
	GP surgery address:			
		l		
٧	Vhat sex where you a	ssigned at bir	th?	
	Male			
	Female			
V	What age are you?			
•	viiat age are you:			
٧	Vhat race/ethnic grou	p do you cons	ider yourself	?
	White British			
	White Other			
	Black Caribbean/Black Ca	ıribbean		
	British			
	Black African/Black Africa	an British		
	Indian/Indian British			
	Pakistani/Pakistani Britisl	h		
	Bangladeshi/Bangladeshi	British		
	Chinese/Chines British			
	Filipino/Filipino British			
	Maghreb / Middle Easter	'n		
	Mixed Ethnicity			
	Other (please specify)			
L)o you have / a histor y Heart Failure	y of any of the	following?	
		ا مسمممیسم)		
	Hypertension (high blood	•		
	Stroke/TIA/thromboemb			
	Vascular disease (prior M	• •		
	artery disease or aortic p	iaque)		
	Diabetes			
	Atrial fibrillation			

Are you taking any of the medication b	e low?
Warfarin	
Dabigatran	
Rivaroxaban	
Edoxaban	
Apixaban	
Beta-blocker (ends in IoI)	
Verapamil	
Diltiazem	
Amiodarone	
Flecainide	
Propafenone	
Digoxin	
Other (please specify)	
Do you have any of the following symp	toms?
Heart palpitations	
Chest pain	
Dizziness	
Fatigue	
Light-headedness	
Shortness of breath	
Reduced ability to exercise	
None	
	Screening
KardioMobile ECG Screening	Result
Sinus rhythm	
AF not suspected by abnormal rhythm	
AF suspected	
AF known prior to screening	
Basic Periodontal Examination	Result
Upper right Upper anterior Upper	1
Lower right Lower anterior Lower	
Lower differior Lower	

Appendix 12 : Follow up telephone screening form Phase 1 Study Protocol Date: 25/1/2022 Version: 5

12.12 Appendix 12: Follow up telephone screening (Version 2: 25/1/2022)

	T
Participant ID:	
Since your screening have	•
a cardiology appointmen	1t?
Yes	
No	
Don't know	
If you were referred, have	
cardiology appointment	:
Yes	
No	
Don't know	
Date in the future	
Have you had a 12 lead I	ECG since your
screening?	
Yes	
No	
Don't know	
Have you been prescribe	and any of the following
medication since your so	
Warfarin	ineerinig:
Dabigatran Rivaroxaban	
Edoxaban	
Apixaban	
Beta-blocker (ends in lol)	
Verapamil	
Diltiazem	
Amiodarone	
Flecainide	
Propafenone	
Digoxin	
Other (please specify)	
Have you been told you	need?
Cardioversion	ileeu:
-	
Ablation	

12.13 Appendix 13: Telephone interview schedule Phase 2 (Version 2: 25/1/2022)

Interview schedule - Gain verbal consent at start of interview

The view schedule – Jani verbai consent at start of										
To explore the views of healthcare professionals (periodontal dentists, nurses and students, and GP involved in the study)										
Initial information collected: profession, sex, length of time in	Initial information collected: profession, sex, length of time in profession.									
Question	Prompts									
1. Tell me about your experience of being involved in the	Warm up question – interviewer to give a brief description of the study if the participant									
Detect AF study	is not clear, including the patient screening process and onward referral pathways.									
	Hospital staff:									
	How did you tell patients about the study?									
	How keen were patients to participate? Why was this?									
	What could be done better to engage more patients?									
	GPs:									
	How many letters did you receive about a patient with AF or an abnormal rhythm									
	because of the study?									
	What did you do when you received a letter about a patient from the study?									
	What could be done to improve the information that your received about your patient									
	(described if not used)?									
2. What do think about the idea of opportunistically	Hospital staff:									
screening for AF during periodontal hospital	How might AF screening be integrated into the appointment itself?									
appointments on a routine basis?	Why is AF screening appropriate in this patient group?									
	GPs:									
	How do you feel about AF screening taking place in locations other than general									
	practice?									
	What effect do you think that this would have on your workload?									
3. What do you think would facilitate the implementation	Dental staff									
of opportunistic single lead ECG/six lead screening for AF	What support tools would need to be in place to remind about screening									
patients over ≥ 65 years in dental hospitals?	What support would be needed to aid diagnosis?									

		What would improve your confidence to implement an AE screening programme in
		What would improve your confidence to implement an AF screening programme in
		periodontal appointments?
		Who would be responsible for screening?
		GPs
		How would you manage communication between the GP surgery and the hospital if
		screening was to be implemented in dental hospitals?
		How confident would you feel about a diagnosis given via this route?
4.	What do you think are the barriers for implementing	Dental staff and GPs
	opportunistic single lead ECG/six lead AF screening for	How much time would screening take?
	patients over ≥ 65 years in dental hospitals?	What about funding?
		Which patients would be more likely to take part?
5.	What would be the ideal onward referral pathway for:	
	a) A patient diagnosed with suspected AF during a	
	periodontal appointment.	
	b) A patient diagnosed with another abnormal ECG	
	trace during a periodontal appointment.	
6.	Is there anything else about the potential for AF	
	screening at hospital periodontal appointments that you	
	wish to share before we finish?	
		1

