- To assess the suitability and cost-effectiveness of AF screening in a dental setting.

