1	This indicates that there are no pockets >3.5mm (i.e. the black band is completely visible), no calculus or plaque traps (e.g. overhanging restorations) but there is bleeding after probing		
2	This indicates that there are no pockets >3.5mm (i.e. the black band is completely visible) but there is calculus or plaque traps present		

Edinburgh Napier

3	This indicates that probing depths between 3.5mm and 5.5mm have
	been found (i.e. black band is partially visible)
4	This indicates a probing depth of >5.5mm (i.e. black band is completely hidden in pocket)
*	Indicates furcation involvement

The study team will provide a list of all participants in an encrypted excel spreadsheet (name, date of birth and address) to allow for identification to the dental hospital staff. The dental hospital will provide the result of the basic periodontal examination for each participant on an encrypted excel spreadsheet. Patients will give written consent for this data to be shared with the study team, and an appropriate data-sharing agreement will be in place between Edinburgh Napier University and Newcastle Dental Hospital.

Phase 2: healthcare professionals' interview:

Upon completion of phase one, healthcare participants will be asked to take part in an individual qualitative telephone interview with an Edinburgh Napier University researcher. A semi-structured interview schedule [Appendix 13] will be referred to in the telephone interview. We will explore the barriers and enablers to the screening processes in the AF detection programme and the effects it has had on the reported practice of the healthcare professionals involved with the participant. At the end of the interview, participants will be emailed a participant debrief sheet [Appendix 10].

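### One hospital-staff prompt in the Phase 2 interview schedule (Appendix 13, question 2) assumes that AF screening is appropriate, which the study says it will determine

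*Combined protocol and SAP*

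**What the plan says.** Appendix 13 has six main questions, with a column of prompts beside them, several split by respondent group. The stem of question 2 is open; it begins "What do think about the idea of opportunistically" and goes on to screening for AF at hospital appointments as a routine. The prompts under it are:

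- Hospital staff: "How might AF screening be integrated into the appointment itself", then "Why is AF screening appropriate in this patient group".
- GPs: one that begins "How do you feel about AF screening taking place in locations other than general" practice, then one on the effect on their workload.

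On how the schedule is used, section 4.1 says: "A semi-structured interview schedule [Appendix 13] will be referred to in the telephone interview". The interviews come after Phase 1 is complete.

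Section 1.3 lists the appropriateness of screening in dentistry among the things the study sets out to determine. Section 2.1 has the secondary objective "To assess the suitability and cost-effectiveness of AF screening in a dental setting".

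**The concern.** A prompt that asks why something is appropriate leaves the respondent two courses: supply reasons, or challenge the interviewer's premise. Someone who doubts that screening belongs in a dental hospital is not invited by that prompt to say so. The premise is also one of the matters under study, so the prompt supplies part of the answer that the interview is meant to elicit.

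At stake is the balance of the qualitative account from hospital staff. The plan has about 20 interviews across staff, students and GPs (section 2.3), analysed thematically. If a prompt has shaped what people said, the analysis has no means of removing that afterwards. The remedy has to come in the wording, before the interviews.

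**Working it through.** No arithmetic applies: the point concerns the wording of a qualitative schedule and depends on no sample size, effect size or error rate. The check is to read every question and prompt in Appendix 13 that bears on appropriateness, and then to set the result against the stated aims.

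**1. The two hospital-staff prompts under question 2.**
- "Why is AF screening appropriate in this patient group" presupposes appropriateness. Only reasons in favour answer it directly.
- "How might AF screening be integrated into the appointment itself" is conditional and concerns logistics. It presupposes at most that integration can be done. A respondent can answer that it could not be fitted in, and nothing in it says that screening is appropriate.

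So one of the two presupposes the answer. Neither asks whether screening is appropriate, or why it might not be.

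**2. The GP prompts under question 2.** Neither presupposes appropriateness. GPs are not prompted on appropriateness in this patient group at all.

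**3. Where else hospital staff could give an unfavourable view.**
- The stem of question 2 allows any opinion.
- Question 3 asks what would help implementation, and question 5 asks for the ideal referral pathway. Both start from screening going ahead.
- Question 4 begins "What do you think are the barriers for implementing" and is put to dental staff and GPs alike. Its prompts cover time, funding and which patients would take part. This invites negative views, although mainly about feasibility.
- Question 6 begins "Is there anything else about the potential for AF" screening and is an open close.

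A sceptical respondent therefore has at least three openings: the stem of question 2, question 4 and question 6. Of these, only the stem of question 2 comes close to asking directly whether screening is a good idea, and the leading prompt sits beneath that stem.

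**4. Against the stated aims.** Section 1.3 treats appropriateness as unknown, and the prompt treats it as known. That contradiction is in the documents and needs no inference. The link to the suitability objective in section 2.1 is weaker. The study design section and section 5.1.2 tie Phase 2 to factors affecting the sustainability of screening, and section 5.1.1 gives its topics as barriers and enablers. The data management plan (Appendix 15, section 2) lists suitability with the Phase 1 data. On the other side, section 5.1.2 specifies no analysis of suitability beyond cost-effectiveness, so the interviews are a plausible source for the rest. No section says that they are.

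**The case against.** The strongest reply is that this is one line in a prompts column, under an open question, in a semi-structured interview that also asks for barriers and ends with an open invitation. Nothing says that each prompt is read out word for word to everyone, and a trained interviewer could phrase it neutrally on the day. That reply stands as a limit on the effect. It does not make the written prompt neutral, and relying on the interviewer to correct it is weaker than correcting the text.

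A reader might infer more than the documents support, in three ways:

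- That both hospital-staff prompts presuppose appropriateness. The integration prompt does not.
- That staff and GP views can no longer be compared fairly, because the two groups are prompted differently. Prompts that differ by role are normal, since the groups do different things in the pathway. The framework analysis in section 5.1.2 compares within and across cases to develop sustainability themes. It plans no contrast between staff and GPs on suitability and no measure of level of support.
- That all 20 interviews could be affected. The 20 include GPs, who do not get this prompt, and no split between the groups is given.

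**Conclusion.** The point holds for one prompt and one respondent group. As written, the prompt is leading on a matter that the study undertakes to determine, and the likely direction of any steer is towards a favourable view. How large that steer would be cannot be computed from the documents. The primary outcome, the secondary correlations and the cost-effectiveness model do not depend on it.

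It would go too far to say that the interview evidence for the suitability objective as a whole is biased. The documents do not assign that objective to Phase 2, and the rest of the schedule leaves room for dissent.

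The conclusion assumes that interviewers use the prompt broadly as written. If they paraphrase it neutrally, the effect disappears. This is a minor wording fault, worth correcting because the correction is small and the opportunity is lost once the interviews have been held.

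**What to change.** Before the Phase 2 interviews, replace the prompt in Appendix 13, question 2, with a neutral one, for example: *Do you think AF screening is or is not appropriate in this patient group, and why?* The integration prompt can stay as it is.

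Putting the same reworded prompt to GPs is optional. It would give both groups one common prompt on appropriateness, but the planned analysis does not require it.

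The cost is a minor amendment to Appendix 13. Under section 9.1 a protocol change needs the principal investigator's approval and authorisation by the School, then NHS REC and local R&D approval. That is some administrative effort for one line, so it would be sensible to submit it with any other pending amendment. Because the interviews follow Phase 1, the planned sequence leaves time for this.
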